## 13. STATISTICS

### 13.1. Description

Data stored in relational databases will be imported into SPSS software for statistical purposes. Statistical analysis will initially be reported in Excel. Data will be investigated for quality using range checks and frequency distribution. Underlying distributions of variables will be tested. Details of statistical analysis are described in Section 13.1.3.

#### 13.1.1. Number of Participants

38 participants will be required to complete the study.

#### 13.1.2. Significance

A p-value less than or equal to 5% will be considered to be statistically significant.

#### 13.1.3. Analysis

Participants who complete the study treatment will be included in the analysis dataset. Reasons and frequency distribution of participants discontinued will be reported.

Data will be summarised as means  $\pm$  standard deviations for variables measured on an interval scale and median  $\pm$  inter-quartile range for ordinal variables. Statistical tests will be employed to determine significant differences in tear parameters, subjective symptoms and other parameters between Optime! Manuka+ Eye Drops and Systane Ultra eye drops. Normality will be assessed using the Shapiro-Wilk test. Independent t-tests will be used for comparison of continuous normally distributed data between the test and control groups. Non-parametric data will be analysed using Mann-Whitney U test. Proportions will be compared using  $\chi^2$  tests and associations will be examined using Pearson's correlation. The level of significance is set at  $\alpha=0.05$ . Statistical analysis will be performed using SPSS software V.22.0. The difference between the 28 days and baseline data will be used to quantify the treatment effect.

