#### 4.2.1. Risks and Benefits

##### Risks of the Clinical Trial

Although unlikely, it is possible that participants may be allergic to any of the ingredients in the study eye drops. Signs of ocular allergy include swelling, redness, itching and watering of the eyes. Subjects with a known allergy to the study eye drops will not be enrolled. Subjects who experience an allergic reaction will be treated by thoroughly rinsing the eye with preservative free unit-dose saline, continuous monitoring until ocular signs and symptoms have returned to normal, and immediate discontinuation from the study. Subjects may also be referred to the Sydney Eye Hospital for treatment, if required.

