## **7.2. Participant Withdrawal**

Participants may be permanently discontinued from the clinical trial for any of the following reasons:

- If, in the Investigator's opinion, it is in the best interest of the participant;
- Persistent clinical trial-related symptoms/complaints that are not correctable;
- Has a serious adverse event/serious adverse event that is eye related and/or which, in the Investigator's opinion, requires withdrawal of the participant;
- Participant voluntarily withdraws consent from the clinical trial (i.e. Revocation of Consent);
- If a participant is not compliant with the clinical trial requirements and instructions;
- Protocol violations/deviations.

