### 12.5. Follow-up

Participants who experience an adverse response will be discontinued from the study and followed up until the condition resolves or the participant is referred to another practitioner.

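### The only defined analysis dataset is treatment completers, so the comparison of drops is not protected by randomisation; separately, the completer target is given as both 38 and 46

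*Combined protocol and SAP*

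**What the plan says.** Section 13.1.3 defines the analysis set in one sentence: "Participants who complete the study treatment will be included in the analysis dataset". The next sentence promises a report of how many participants were discontinued and why. No all-randomised, all-dispensed or safety set appears elsewhere.

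The ways out of that set after randomisation are these:

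- Section 7.2 opens with "Participants may be permanently discontinued from the clinical trial for any of the following reasons". Its list includes "Persistent clinical trial-related symptoms/complaints that are not correctable", "If a participant is not compliant with the clinical trial requirements and instructions", "Protocol violations/deviations" and the investigator's view that "it is in the best interest of the participant". It also covers serious events and withdrawal of consent.
- Section 12.5: "Participants who experience an adverse response will be discontinued from the study". The term for the response is not defined.
- Section 4.2.1, on allergic reaction, ends with "and immediate discontinuation from the study".

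Section 7.3 exits participants on request and describes no day-28 assessment for them. Section 13.3 omits missing values variable by variable; it does not return non-completers to the dataset.

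On numbers, 4.2.4 and 13.1.1 require 38 completers, and 4.2.4 plans about 48 enrolled at 20% dropout. Section 6.1.3 requires 46 completers.

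**The concern.** Randomisation makes the two groups comparable at the start. A comparison restricted to those who finish treatment keeps that protection only if finishing is unrelated to the assigned drop or unrelated to outcome. Here several reasons for leaving depend on how well the assigned drop is tolerated, and the two drops differ in composition (4.2.2). Section 12.4.2 foresees stinging, redness and blurred vision, and 4.2.4 allows for 20% loss, so the case is not remote.

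If more people leave one arm, and those who leave would have done worse, the completer comparison favours the less tolerated drop. If they would have done better, it favours the other. The concern is greater for OSDI symptoms (secondary) than for lipid layer thickness (primary, instrument-measured). Day-28 values that are not sought at the time cannot be obtained later.

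The two completer targets are a separate defect: correcting one problem leaves the other in place.

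**Working it through.** **1. The plan's own enrolment figure.** Inputs: 38 completers and 20% dropout (4.2.4, 13.1.1). Enrolment = completers / (1 − loss) = 38 / 0.80 = 47.5, rounded up to 48. This reproduces the plan's 48. The 38 itself cannot be reproduced, because no effect size, SD or power is stated.

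**2. The other target.** 46 / 0.80 = 57.5, rounded up to 58, which does not match 48. If 46 of 48 must complete, only 2 may be lost: 2 / 48 = 4.2%, not 20%. One possible origin is 38 × 1.20 = 45.6, rounded up to 46, an enrolment figure labelled as completers; this is inference only.

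**3. How large the selection effect could be.** The documents give no loss by arm and no relation between loss and outcome, so everything in this step is assumed. Let tolerance and outcome be bivariate normal with correlation r, with no treatment effect. Allocation is taken as equal, 24 per arm, which treats all 48 as randomised. A participant completes if tolerance exceeds the p-quantile, where p is the loss in that arm. The completer mean is then shifted by r × φ(z_p) / (1 − p), in SD of the outcome, and

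bias = r × [φ(z_p1) / (1 − p1) − φ(z_p2) / (1 − p2)].

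- 20% v 10%: the bracket is 0.350 − 0.195 = 0.155.
- 30% v 5%: the bracket is 0.497 − 0.109 = 0.388.
- 20% v 20%: the bracket is 0.

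Type I error comes from simulated trials using a two-sided pooled t-test in completers at 0.05.

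| Loss by arm | Losses related to tolerance | Bias in SD, r = 0.3 / 0.5 / 0.7 | Type I error |
|---|---|---|---|
| 20% v 20% | all | 0 / 0 / 0 | about 5% |
| 20% v 10% | all | 0.05 / 0.08 / 0.11 | 5.2 / 5.7 / 6.5% |
| 20% v 10% | half | 0.03 / 0.04 / 0.06 | 5.1 / 5.2 / 5.3% |
| 30% v 5% | all | 0.12 / 0.19 / 0.27 | 6.5 / 9.2 / 14.2% |
| 30% v 5% | half | 0.06 / 0.11 / 0.15 | 5.4 / 6.2 / 7.3% |

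In the half rows, only half of each arm's loss depends on tolerance and the rest is unrelated to outcome, so p in the formula is halved: 0.195 − 0.109 = 0.086 for 20% v 10%, and 0.274 − 0.060 = 0.214 for 30% v 5%. At r = 0.1 with all losses driven by tolerance, type I error is at most 5.1% in both unequal scenarios. Simulation error is about 0.1 to 0.2 percentage points.

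**4. Discontinuation wording.** Section 12.5 makes discontinuation mandatory after an undefined response. Section 7.2 makes it permissive. Section 4.2.1 makes it immediate for allergic reaction. Who remains in the 13.1.3 dataset depends on which reading is followed.

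**The case against.** The strongest reply has four parts.

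First, 13.1.3 does not say that the dataset is limited to completers, and it does promise to report discontinuations. That stands as a matter of wording. But no other set is defined, and disclosing the loss does not correct the comparison.

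Second, the objectives and endpoints concern daily use for about a month (synopsis, 6.2, 6.3). Including people who stopped drops answers a different question. This stands, and the change must say so openly; it does not make the completer comparison free of selection.

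Third, the larger figures need every loss to be driven by tolerability and a sizeable correlation. Section 7.2 also lists non-compliance, deviations and withdrawal of consent, and nothing in the documents supports r of 0.5 to 0.7 for change in lipid layer thickness. This stands, and is why the milder rows are shown.

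Fourth, safety. A reader might infer that safety information on those who leave is lost. The documents do not support that: adverse events are followed to resolution (12.2) and listed (12.4), and dispensing is tracked (10.2.2). Nor is safety reporting expressly tied to the 13.1.3 dataset. What remains is conditional: if day-28 acuity and biomicroscopy are compared in that dataset, the same selection applies to them.

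A reader might also infer from 6.1.5, which counts enrolment from consent, that the 20% allowance has to absorb screening failures. The text does not settle this. Sections 4.2.1 and 7.1 use enrolment in the sense of eligible participants, and 4.2.4 speaks of dropout and of an approximate 48. The protocol should say what 48 counts; no shortfall is shown.

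**Conclusion.** The concern holds as a gap in the plan, one that should be fixed. Confidence is high on the text and on the arithmetic for 38 and 46. It does not extend to any claim that the result will be materially biased: that requires loss that differs by arm and is related to outcome, and the documents supply neither figure. A reader might take the 14.2% type I error as the expected size of the problem. It is the extreme end of an assumed range, which runs from no bias under equal loss, through 5.2% to 6.5% at 20% v 10%, to 6.5% to 14.2% at 30% v 5%, the last falling to 5.4% to 7.3% if half the losses are unrelated to outcome.

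The conflict between 38 and 46 needs no assumption. It is a separate correction and adds no weight to the analysis-set point.

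**What to change.** 1. **13.1.3.** Make the primary efficacy set all randomised participants, analysed as randomised. Seek day-28 data from those who stop drops and are willing to attend. Keep completers as a sensitivity analysis. State in 5.1, 6.2 and 6.3 that the primary comparison is of assigned drops and that the completer analysis addresses effect under daily use.
2. **13.3.** State the missing-data assumption. With only two visits, imputation from arm and baseline cannot by itself correct tolerability-related loss. Add a sensitivity analysis that shifts imputed day-28 values by arm over a stated range (0 to 0.5 SD, for example) and reports where the conclusion changes.
3. **Safety and discontinuations.** Report adverse events and discontinuations by arm in everyone dispensed drops, with the 10.2.2 tracking record as denominator.
4. **Wording.** Reconcile 12.5 with 7.2 and 4.2.1 on whether discontinuation is mandatory or permitted, and define the response that 12.5 refers to. No clinical rule is proposed.
5. **Separate correction.** Reconcile 38 and 46 into one completer target consistent with 48 and 20% loss, and state whether 48 counts consented or randomised participants.

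Cost: amended wording, ethics committee approval before implementation (15.1.3), a few day-28 visits and some extra analysis. New observed data come only from people who stop drops and still attend; for the rest, the primary estimate relies on the stated missing-data assumptions.

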### 4.2 Summary

This study is potentially significant in its demonstration of the benefits of Manuka honey eye drops in altering the physiological properties of the tear film, thereby improving ocular comfort and reducing dry eye. These findings will aid in informing practitioners about the benefits of considering Manuka eye drops in the alleviation and treatment of dry eye disease, whilst adding credibility to the Optimel Manuka eye drops range and growing its potential market opportunities globally.

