### 5.2. *Clinical Hypothesis*

We hypothesize that the:

- Measurable differences in the subjective symptomatology and in objective tear film parameters will be apparent after 4 weeks of use with the Optimel Manuka and Systane Ultra eye drop treatments.

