## 6.2. Primary Endpoint

The primary endpoint is a measurable difference in tear lipid layer thickness between Optimel Manuka eye drops and Systane Ultra eye drops after 4 weeks of daily use.

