## 6.3. Secondary Endpoint(s)

The secondary endpoints are: a measurable difference in tear parameters such as tear breakup time and tear evaporation rate, and subjective symptoms after 4 weeks of daily use.

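### With lipid layer thickness as the only primary, every secondary and unnamed parameter is still declared significant at an unadjusted 5%, and section 11.1 lets a secondary alone count as efficacy

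*Combined protocol and SAP*

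**What the plan says.** Section 6.2 sets one primary: "The primary endpoint is a measurable difference in tear lipid layer thickness between Optimel Manuka eye drops and Systane Ultra eye drops". Section 6.3 lists as secondary "a measurable difference in tear parameters such as tear breakup time and tear evaporation rate, and subjective symptoms after 4 weeks of daily use". That names three variables, but the words 'such as' leave the list open. Section 11.2 says symptoms are measured with the OSDI, while section 6 lists a symptom survey beside the OSDI at both visits.

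One significance rule covers everything. Section 13.1.2 reads: "A p-value less than or equal to 5% will be considered to be statistically significant". Section 13.1.3 repeats alpha 0.05 and sets the scope: "Statistical tests will be employed to determine significant differences in tear parameters, subjective symptoms and other parameters". It adds chi-square tests and Pearson correlations without saying how many.

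Section 11.1 describes the efficacy parameter as a difference in symptoms, joined by and/or to lipid layer thickness or break-up time. Section 5.2 puts symptoms and tear film measures in one hypothesis: "Measurable differences in the subjective symptomatology and in objective tear film parameters will be apparent after 4 weeks of use".

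No section gives a testing order, an alpha adjustment, or a statement that secondaries are supportive or exploratory.

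**The concern.** Sections 6.2 and 6.3 rank the endpoints, but the ranking does no work later. Section 13 treats all p-values alike. Section 11.1 offers alternatives, any one of which satisfies its wording, and two of them (symptoms and break-up time) are secondary under 6.3. A report could follow the plan to the letter, find no difference in lipid layer thickness, find p = 0.04 on break-up time, and state that the drops differ significantly in efficacy.

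That conclusion would rest on one success picked from several attempts, so its chance of being false is larger than the 5% printed beside the p-value. Because 6.3 and 13.1.3 do not fix the number of attempts, a reader of the results could not work out how much larger.

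**Working it through.** **Inputs**
- Per-test alpha: 0.05 (13.1.2, 13.1.3).
- Named secondaries: k = 3, namely break-up time, evaporation rate and symptoms (6.3). If the symptom survey in section 6 is analysed apart from the OSDI, k = 4.
- Completers: 38 (4.2.4, 13.1.1), taken as 19 per arm. A 1:1 ratio is an assumption, since 6.1.2 gives none.
- Sidedness is not stated for the tests in 13.1.3 ("Independent t-tests will be used for comparison of continuous normally distributed data between the test and control groups"); two-sided is assumed.
- Correlation between endpoints is not in the documents, so a range is shown.
- All figures assume no true difference on any endpoint in the set.

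**The plan's own figure.** The plan states no family-wise error rate, so there is none to reproduce.

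**Step 1: independent tests.** P(at least one false positive) = 1 − (1 − 0.05)^k.
- k = 3: 1 − 0.95³ = 1 − 0.8574 = 0.1426, or 14.3%.
- k = 4: 1 − 0.95⁴ = 1 − 0.8145 = 0.1855, or 18.5%.

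**Step 2: correlated tests.** With a common correlation ρ, each z-statistic is √ρ·U + √(1−ρ)·e, where U is a shared standard normal variable and e is specific to the test. With c = 1.96:

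P = 1 − ∫ φ(u) · [Φ((c − √ρ·u)/√(1−ρ)) − Φ((−c − √ρ·u)/√(1−ρ))]^k du

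| ρ (assumed) | k = 3 | k = 4 |
|---|---|---|
| 0 | 14.3% | 18.5% |
| 0.3 | 13.6% | 17.4% |
| 0.5 | 12.5% | 15.6% |
| 0.8 | 9.8% | 11.4% |
| 0.9 | 8.4% | 9.4% |

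**Step 3: check at the trial's size.** Simulating 100,000 trials of three t-tests with 19 per arm gives 14.4%, 13.5% and 12.7% at correlations 0, 0.3 and 0.5. The normal approximation is adequate here.

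**Step 4: the open list.** The number of other parameters is not given, so no figure can be fixed. Purely as an illustration, six tests would give 1 − 0.95⁶ = 26.5% if independent and 20.7% at correlation 0.5.

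**Step 5: what formal adjustment would do.** Bonferroni over three secondaries uses 0.05/3 = 0.0167 for each test. The family rate becomes 1 − (1 − 0.0167)³ = 4.9% if independent, and 4.4% at correlation 0.5 by the Step 2 integral. The price is power: with 19 per arm, a difference of 0.93 SD has 80% power at 0.05 but about 64% at 0.0167, which is also the first step of Holm's method.

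**The case against.** The best defence is that the plan does have a hierarchy. Sections 6.2 and 6.3 separate one primary from the secondaries, and many readers would take secondaries as supportive without being told. The 5% in 13.1.2 is a per-comparison threshold, and each test does meet it. No section promises 5% across the secondaries. This is a small single-centre comparison of two commercially available products, so strict control over secondaries may be more than it needs.

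Much of that stands. A reader might infer that the trial's false-positive rate is about 14% where 5% was promised. The documents do not support that, because the lipid layer test keeps its own 5% error and no family-wise rate is stated. Nor is there a single correct percentage, since the documents give no correlation and no count of tests.

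A reader might also take section 4.2 as a planned symptom claim: "These findings will aid in informing practitioners about the benefits of considering Manuka eye drops in the alleviation and treatment of dry eye disease". It is background text, ties no claim to any p-value, and cannot carry that weight. Section 5.2 likewise states an expectation and gives no rule that one significant variable is enough.

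A formal hierarchy has a real cost as well. Holm's first step lowers power, and a fixed sequence behind the primary would bar any confirmatory symptom finding if lipid layer thickness shows no difference.

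The defence does not answer section 11.1. Its and/or wording lets a secondary stand in for the primary, which undoes the ranking in 6.2 and 6.3.

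One further point is separate. The synopsis lists lipid layer thickness, evaporation rate and break-up time together as the primary efficacy variable. That conflict needs its own resolution, and settling it in favour of 6.2 leaves the present gap open.

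**Conclusion.** The concern holds as a gap in how secondary results may be interpreted. Taking 6.2 as the governing statement, sections 13.1.2, 13.1.3 and 11.1 together permit an efficacy conclusion from any one of the symptom or break-up time results after a null primary. For the three named secondaries the false-positive chance is 14.3% under independence and stays above 5% at every correlation examined (8.4% even at 0.9). These figures rest on two-sided tests, equal correlation and no true differences. The rate rises by an amount that cannot be stated once the unlisted parameters are tested. The validity of the lipid layer test itself is not in question. The plan should be changed because the change alters what the trial may conclude and costs almost nothing.

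**What to change.** - **13.1.2 and 13.1.3:** state that only the between-group comparison of lipid layer thickness is confirmatory at 5%.
- **6.3:** close the list to tear break-up time, tear evaporation rate and OSDI, and delete 'such as'.
- **11.1:** align with 6.2 by removing the and/or wording, so that lipid layer thickness alone carries the efficacy conclusion.
- **13.1.3:** report the three secondaries as supportive, and other parameters and correlations as exploratory, each with an estimate, 95% confidence interval and nominal p-value.

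A fixed sequence or Holm's method across the secondaries after a significant primary is optional. If it is chosen, the order or method should be written down before unmasking and the power loss shown above accepted knowingly.

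The cost is a few sentences, with no extra data, visits or participants. The downside is that, if the primary fails, a secondary with p of 0.05 or less cannot be claimed as confirmatory.

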**Table 4: Data requirements**

| Procedures/ Data (Y/N)                         | Visit 1
Screening / Baseline | Visit 2
28 days ± 4 days |
|---|---|-------------------------------------|
| Informed Consent                                      | Y                                       | N                                   |
| Meet Inclusion/Exclusion Criteria                     | Y                                       | N                                   |
| Ocular and Medical History, Medications, Demographics | Y                                       | Y                                   |
| Vision Tests (Visual Acuity)                          | Y                                       | Y                                   |
| Randomization (to eye drop)                           | Y                                       | N                                   |
| Slit-Lamp Biomicroscopy                               | Y                                       | Y                                   |
| Subjective questionnaire                              | Y                                       | Y                                   |
| Tear evaporation rate                                 | Y                                       | Y                                   |
| Tear break-up time                                    | Y                                       | Y                                   |
| Tear lipid layer thickness                            | Y                                       | Y                                   |

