### 6.1.3. Clinical Trial Population

A total of 46 participants with dry eye disease will be required to complete the study.

Trial participants will be recruited from the local population at the investigational site. An e-mail invitation will be circulated to [REDACTED]

[REDACTED]

[REDACTED]. Advertisements may also be posted in [REDACTED]

[REDACTED]

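### Section 13.1.3 compares the arms on change from baseline with no baseline covariate: valid, but ANCOVA would usually be more precise at almost no cost

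*Combined protocol and SAP*

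**What the plan says.** Section 13.1.3 is the only specification of the analysis. For the between-arm comparison it says "Independent t-tests will be used for comparison of continuous normally distributed data between the test and control groups" and "Non-parametric data will be analysed using Mann-Whitney U test". It closes with "The difference between the 28 days and baseline data will be used to quantify the treatment effect". The text does not join the tests to that last sentence, but the natural reading is that the tests are applied to the change score. No section mentions ANCOVA, regression or any baseline covariate.

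The primary endpoint in Section 6.2 is a "measurable difference in tear lipid layer thickness between Optimel Manuka eye drops and Systane Ultra eye drops after 4 weeks of daily use". It does not say whether the quantity compared is the Week-4 value or the change.

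The baseline values needed for adjustment are already collected. Table 4 (Section 6.1.1) schedules "Tear lipid layer thickness", break-up time, evaporation rate and the questionnaire at both visits, although Sections 6 and 9.2 describe evaporation rate as a procedure that may be done.

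On size, Section 13.1.1 says "38 participants will be required to complete the study", and Section 4.2.4 agrees. Section 6.1.3 says "A total of 46 participants with dry eye disease will be required to complete the study". The significance rule in Section 13.1.2 is "A p-value less than or equal to 5% will be considered to be statistically significant", with no statement of one or two sides.

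**The concern.** A change-score test does use baseline, but it assumes that each unit of baseline carries over as exactly one unit at Week 4. With similar SDs at the two visits and a correlation below 1, the true slope is below 1. Two things follow.

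- **Precision is lost.** Part of the baseline noise is added to the outcome instead of being removed. In a trial this small that widens the interval for the primary endpoint.
- **Chance imbalance is over-corrected.** The estimate is unbiased over all randomisations. Given the imbalance that actually occurs, however, it is shifted in a predictable direction.

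The wording also leaves open whether the tests will be run on changes or on Week-4 values. In the second case baseline would not be used at all. With baseline as covariate, ANCOVA gives the same treatment estimate for either response, so naming it settles that choice.

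**Working it through.** **Inputs from the plan.** 38 completers (Sections 4.2.4 and 13.1.1) or 46 (Section 6.1.3); 5% significance (Section 13.1.2); two randomised arms (Section 6.1.2).

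**Assumptions not in the plan.** 1:1 allocation (19 per arm), a two-sided test, correlation r between baseline and Week 4 from 0.3 to 0.9, and at first the same SD, s, at both visits.

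**The plan's own figure.** 38 / (1 − 0.20) = 47.5, which rounds up to the 48 to be enrolled. The 38 itself cannot be reproduced, because no effect size, SD or power is given.

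**Step 1: variance per participant.** Let β be the slope of Week 4 on baseline.

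- Change score: Var = residual variance + (β − 1)² × baseline variance. With equal SDs this is 2s²(1 − r).
- ANCOVA: residual variance, s²(1 − r²), times 1 + 1/(N − 4) for estimating the slope. That factor is 35/34 = 1.029 at N = 38 and 43/42 = 1.024 at N = 46.
- Ratio, ANCOVA to change score: (1 + r)/2 × [1 + 1/(N − 4)].

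Since (β − 1)² cannot be negative, ANCOVA can lose only through the factor of about 1.03, whatever the two SDs are.

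**Step 2: results with equal SDs.** The first, third, fourth and fifth result rows are for 38 completers. Detectable differences are for 80% power, from the noncentral t with 36 df (change) and 35 df (ANCOVA), in single-visit SD units.

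| | r = 0.3 | r = 0.5 | r = 0.7 | r = 0.9 |
|---|---|---|---|---|
| Variance ratio, N = 38 | 0.669 | 0.772 | 0.875 | 0.978 |
| Variance ratio, N = 46 | 0.665 | 0.768 | 0.870 | 0.973 |
| CI width ratio | 0.82 | 0.88 | 0.94 | 0.99 |
| ANCOVA power where the change score has 80% | 93% | 89% | 85% | 81% |
| Detectable difference, change to ANCOVA | – | 0.93 to 0.82 | 0.72 to 0.68 | 0.42 to 0.41 |

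Break-even is at r = 2/1.0294 − 1 = 0.943 for N = 38 (0.953 for N = 46). At r = 0.5, 38/0.772 = 49.2, so 38 completers analysed by ANCOVA give about the precision of 49 analysed by change score.

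**Step 3: simulation (20,000 trials per setting, 19 per arm).** Type I error was 4.8% to 5.0% for the change-score t-test and 4.7% to 5.1% for ANCOVA. Simulated variance ratios under the null were 0.66, 0.78, 0.88 and 0.97, in line with the formula.

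**Step 4: unequal SDs.** With k = Week-4 SD / baseline SD, the ratio is k²(1 − r²)/(1 + k² − 2rk) × 1.029.

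| | r = 0.3 | r = 0.5 | r = 0.7 | r = 0.9 |
|---|---|---|---|---|
| k = 0.8 | 0.52 | 0.59 | 0.65 | 0.63 |
| k = 1.3 | 0.83 | 0.94 | 1.02 | 0.94 |

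**Step 5: chance imbalance.** The SD of the baseline difference between arms is √(2/19) = 0.32 of a single-visit SD (√(2/23) = 0.29 with 46). It exceeds 0.5 SD in about 12% of randomisations (9% with 46). With equal SDs, an imbalance of 0.5 SD shifts the change-score estimate by 0.5(1 − r): 0.25, 0.15 and 0.05 SD at r = 0.5, 0.7 and 0.9.

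**Step 6: if the tests are run on Week-4 values.** The variance ratio of ANCOVA to the t-test is (1 − r²) × 1.029 = 0.94, 0.77, 0.53 and 0.20 at r = 0.3, 0.5, 0.7 and 0.9.

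**The case against.** The strongest reply is that nothing is wrong: the planned test is valid and uses baseline, and the choice lies between two acceptable analyses. The plan gives no correlation or SD, so the benefit here is unknown. On the scale a reader sees, interval width falls by only 6% at r = 0.7 and 1% at r = 0.9. All of this stands, and it limits the size of the claim. It does not remove the asymmetry between a loss of about 3% in variance at worst and a gain of 12% to 33% for r between 0.7 and 0.3 under equal SDs.

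Four narrower points also stand in part.

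- **OSDI.** Entry requires a minimum score (Section 7.1.1), which cuts off the lower end of baseline and reduces the gain. If it halved the baseline variance (an assumption), the ratio would be (1 + r)/[(1 + r) + 0.5(1 − r)] × 1.029 = 0.81, 0.88, 0.95 and 1.00 at r = 0.3, 0.5, 0.7 and 0.9, where r is the correlation before the cut-off. Lipid layer thickness is not directly affected.
- **Mann-Whitney route.** The figures above apply to the t-test only; no efficiency figure was derived for the rank test.
- **Non-normal residuals.** A fallback with no stated trigger would let the data choose the primary analysis. A rank-based model also does not give an adjusted mean difference.
- **Unit of analysis.** The model needs one baseline and one Week-4 value per participant. Section 11.2 takes three break-up time readings in each eye, so that rule must be set as well. Averaging would tend to raise r and shrink the gain.

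The Week-4 reading in step 6 is the less likely one, and the case does not depend on it.

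**Conclusion.** The concern holds as a recommended improvement, not as an error. The planned comparison has correct type I error and is unbiased over randomisations. Under equal SDs and 1:1 allocation, adjusting for baseline narrows the interval by roughly 18% to 1% as r goes from 0.3 to 0.9, and the gain disappears above about r = 0.94. If the Week-4 SD is smaller than the baseline SD the gain is larger; if it is larger, the gain can be small or absent. The actual gain cannot be stated, because neither the correlation nor the SDs are given. Using 46 completers in place of 38 barely changes the ratios, so the conflict between those figures does not affect this conclusion, although the sections should be reconciled.

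**What to change.** Add to Section 13.1.3, before unmasking, text along these lines:

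> The primary analysis is a linear model (ANCOVA) of Week-4 lipid layer thickness on treatment, with baseline lipid layer thickness as covariate. The adjusted mean difference between arms is reported with its 95% confidence interval.

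Then:

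- Use the same model for break-up time, evaporation rate and OSDI, each with its own baseline.
- Keep the change-score t-test or Mann-Whitney U test as sensitivity analyses.
- Check the residuals. State in advance what would trigger a transformed or rank-based ANCOVA, and what would then be reported in place of the mean difference.
- State how eyes and repeat readings are reduced to one value per participant and visit. This is a separate issue, but the model depends on it.
- Align the primary variable. The wording above follows Section 6.2, whereas the synopsis lists lipid layer thickness, evaporation rate and break-up time together.

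The cost is a few sentences, one degree of freedom (36 to 35, which raises the critical t value by 0.1%) and at most about 3% in variance. The SPSS software already planned can fit the model. No new data or visits are needed.
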